**2. What are the statistical considerations for the protocol?**

The objectives section and the statistical section should correspond, and any objective for which analysis is unfeasible should be deleted. Also, the estimates and non-statistical assumptions of the statistical section should be supported by discussion in the background section.

The answer to this question should include:

- Study Design/Endpoints
- Recap of study objectives and endpoint definitions. An assessment of how study objectives will be assessed by identifying & defining which endpoints will be used to assess each component of the study objectives.
- The study design should include contingencies for early stopping, interim analyses, stratification factors (if applicable), and any characteristics to be incorporated in analyses.
- The power/precision of the study to address the major study endpoint(s), the assumptions involved in the determination of power/precision.
- If statistical hypothesis testing is included then specify the null and alternative hypotheses, the test statistic, and the type I and II error rates
- If precision of an estimate, then provide a definition for precision
- If other, then specify

Answer/Response:

Following an initial visit (in outpatient clinic) for consent administration and screening, participants will be asked to return for a pre-assessment visit involving a battery of gold-standard UE function tests including: the Fugl-Meyer assessment of UE motor function (FMUE); the Wolf Motor Function Test (WMFT) assessment of UE motor function; the Box and Blocks Test; and the Motor Activity Log (MAL). Permuted block randomization will be employed. Subjects assigned to GRASP HEP will be asked to employ the GRASP system for UE practice at home over an 8-week period. Patients in the UCT group will not receive any treatment through the study and will continue to receive any previously prescribed therapy services. After 8 weeks, all participants will be asked to return for a post-assessment visit repeating the same battery of tests. Additionally, subjects will be asked to respond to a set of questionnaire-based instruments including the System Usability Scale (SUS); a technology acceptance model (TAM) questionnaire; and a Player Experience of Needs Satisfaction (PENS) questionnaire; and participate in a structured interview.

The pre- to post-intervention change in the composite assessment scores will be the primary endpoint for the GRASP Phase II study. Pre-intervention scores will be subtracted from post-intervention scores to produce a set of delta values which will be analyzed via Analysis of Covariance. One null hypothesis will test if the mean pre- to post-intervention change in scores is equal to zero, while the second null hypothesis will test if the mean pre- to post-intervention change in scores is the same between groups. For both null hypotheses, a  $p \leq 0.05$  decision rule will be utilized as the rejection criterion.

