#### ► IF YES, describe the stratification/ randomization scheme.

##### INSTRUCTIONS:

The stratification factors and/or the randomization plan should be identified. If there is no randomization component or important patient characteristics that will be used in treatment allocation or data analysis, a statement to this effect should be included.

Stratification factors: These are pretreatment patient characteristics which could be balanced across treatment arms by design or may be used to determine starting dose or treatment allocation.

If randomization is going to be used, the details of the randomization plan should be described.

The description should include:

- the method and timing of randomization
- the type of randomization scheme that will be used in the study
- whether or not the randomization masked/blinded/if so, then to whom is it masked/blinded
- who has access to the randomization scheme

Answer/Response:

**To ensure that an approximately equal number of subjects are randomized to the GRASP HEP and UCT groups throughout the Phase II enrollment period, we will randomly assign the patients to the two study-groups in accordance with a permuted block randomization scheme. The randomization list will be generated by PLAN procedure of SAS (SAS Institute Inc., Cary, NC).**

**The group assignment will be blinded to the therapists (raters) who perform the pre- and post-assessments. The group assignment will be not be blinded to the participants.**

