#### **GRASP HEP Home Visit 3 (will last about 90 minutes)**

- At the end of the 8-week HEP period, a non-blinded study therapist will conduct a home visit at the patient's residence to observe patients' independent use of the system and recover the system hardware.
- Participants will respond to questionnaire-based instruments including the System Usability Scale (SUS), a technology acceptance model (TAM) questionnaire, and a Player Experience of Needs Satisfaction (PENS) questionnaire, as well as participate in a structured interview. These assessments will be audiotaped.

The participant will be encouraged to invite his or her home care provider (e.g. spouse or family member, if applicable) to attend the GRASP HEP visits, so that this individual is able to assist the patient during independent practice.

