#### **ALL – Final Outpatient Visit at UVA: Post-Assessment (will last about 90 minutes)**

- Study therapist will administer the same battery of tests used in pre-assessment.
- If administration of the test instruments cannot be completed for any reason (e.g. subject becomes fatigued), the participant may be asked to return for an

additional visit to complete the procedures. The participant will be provided the normal per-visit stipend for the additional visit.

A graphical summary of the GRASP Phase II study is provided below.

2. If this protocol involves study treatment, explain how a subject will be transitioned from study treatment when they have completed their participation in the study.

**Example:** If the subject will be taking an investigational drug, will they need to be put back on an approved drug when they have completed the study? If yes, explain how this will be accomplished and who will cover the cost. If the subject has a device implanted will it be removed? Again- who will cover the cost of the removal?

**Instructions:** Answer NA if this study does not involve a study treatment.

Answer/Response:

At the conclusion of this study, participants assigned to the GRASP HEP group will stop using the GRASP system. No further transition is needed.

To promote equipoise, participants in the UCT group will be offered free access to the GRASP software system following completion of the study. The GRASP systems will be made available to UCT participants for 8 weeks, once the units are no longer needed for the GRASP HEP-assigned participants.

If the UCT participant wishes to take advantage of this offer, when a system becomes available, a study therapist will conduct a home visit at the participant's residence to assist in system setup and training to safely and successfully use the system at home. A study staff member will recover the system after an 8 week period.

**If on the study therapist's recommendation, the study PI determines an additional visit is warranted to ensure a patient can safely and successfully use the system at home, an additional home visit will be conducted.**

**All participants (both GRASP HEP and UCT) will be able to keep the SaeboGlove (without the GRASP system) following completion of the protocol.  
(<https://www.saebo.com/shop/saeboglove/>)**

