**2. Explain your plans for training and oversight of these personnel.**

Answer/Response:

For the purposes of this study, [name] (OTR/L, DOT) will fall under the supervision of the GRASP Phase II PI, [name], UVA PM&R.

In supporting the above described role of remote monitoring and remote check-ins with study participants, [name] will closely coordinate with the GRASP study coordinator and the non-blinded study therapist conducting the GRASP HEP home visits.

[name] is highly experienced in conducting IRB-supervised research, having served as study staff on multiple previous UVA IRB-HSR protocols of similar scope (notably 16117 and 17591). She is very well-versed in the details and procedures of the GRASP Phase II protocol, and in human subject protections.

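### GRASP usability questionnaires are answered, and by the text audiotaped, at a home visit run by a non-blinded therapist, which could tilt the uncontrolled usability result favourably

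*Combined protocol and SAP*

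**What the plan says.** Two parts of the combined protocol and SAP describe the usability instruments.

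- **Statistical Considerations, question 2.** The design summary says "After 8 weeks, all participants will be asked to return for a post-assessment visit repeating the same battery of tests". Its next sentence begins "Additionally, subjects will be asked to respond to a set of questionnaire-based instruments including the System Usability Scale (SUS" and goes on to TAM, PENS and a structured interview. It does not say which arm, at which visit, or who gives the forms.
- **Study Procedures, GRASP HEP Home Visit 3.** At the end of the eight weeks, "a non-blinded study therapist will conduct a home visit at the patient's residence to observe patients' independent use of the system" and to collect the hardware. Under the same visit: "Participants will respond to questionnaire-based instruments including the System Usability Scale (SUS), a technology acceptance model (TAM) questionnaire", then PENS and the interview. The item closes with "These assessments will be audiotaped".

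The procedures for the usual-care group list no questionnaire. The final outpatient visit lists only the motor tests: "Study therapist will administer the same battery of tests used in pre-assessment". The appendix on non-UVA personnel mentions "the non-blinded study therapist conducting the GRASP HEP home visits", in the singular.

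**The concern.** The third hypothesis is directional: it expects stroke survivors to find GRASP usable and to accept it well. The evidence is what GRASP users say about the system. Under Home Visit 3 they say it while a member of the study team is in the home, at a visit that also includes being watched using the system, and with their answers on tape. A respondent in that position may soften criticism. The likely direction is towards higher usability and acceptance, which is also the direction of the hypothesis.

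Only the GRASP arm has used the system by week 8, so no control group shares the same pressure and cancels it. At stake is the credibility of the usability and acceptance claim, not the efficacy result.

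**Working it through.** The plan gives no figure on this point, so the check sets the passages side by side and then asks how a response bias would act.

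**Step 1. Who answers, where, with whom, and on tape?**

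| Place in the document | Arm | Visit | Staff | Taped |
|---|---|---|---|---|
| Statistical Considerations, question 2 | subjects, not specified | not stated | not stated | not stated |
| GRASP HEP Home Visit 3 | GRASP | Home Visit 3 | non-blinded therapist conducts the visit; administrator of forms not stated | yes |
| UCT group procedures | usual care | none listed | – | – |
| Final outpatient visit | all | motor tests only | study therapist | – |

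The only place that assigns the instruments to a visit is Home Visit 3. The design summary is looser than the procedures but does not assign them elsewhere.

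**Step 2. What does the taping cover?** The taping sentence is plural and directly follows a sentence that lists the three questionnaires and the interview. Read literally, it covers all four.

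**Step 3. Is the therapist the trainer?** Home Visits 1 and 2, where the participant is taught, and Home Visit 3 each refer to a non-blinded therapist without saying that it is the same person. The singular phrase in the appendix suggests one person but sets no staffing rule. The link is possible, not established.

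**Step 4. How would a favourable lean act?** Write each observed score as Y = U + b, where U is the answer the participant would give in private and b is the shift caused by the setting. Then

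mean(Y) = mean(U) + mean(b).

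If every respondent shifts by b, the mean shifts by b. If only a share f does so, it shifts by f × b. Sample size does not enter. Table 1 of the protocol puts the arm at 20 with full retention and 16 at 80%. Going from 16 to 20 multiplies the standard error by √(16/20) = 0.89 and leaves the bias unchanged. A comparator with the same exposure would give b − b = 0, but there is none.

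**Step 5. Size.** The documents give no value for b or f and no basis for a plausible range, so no estimate is offered.

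**Step 6. Reach.** The Fugl-Meyer score is taken at the outpatient visit, and the randomization section says "The group assignment will be blinded to the therapists (raters) who perform the pre- and post-assessments". The Home Visit 3 questionnaires play no part in that scoring.

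**The case against.** The case for leaving the plan alone has four parts.

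- **The plan does not say that the therapist reads out or collects the forms.** Its wording is compatible with self-completion, and taping adds little if the forms are filled in on paper. This is fair, but privacy is not provided for either, and the literal text tapes the questionnaires.
- **No decision depends on the result.** The plans for primary and secondary analysis give no test or threshold for SUS, TAM or PENS, so no stated conclusion could flip. This stands, and it keeps the point minor. The missing analysis is a gap of its own. Usability is still a hypothesis that the trial will report on.
- **Self-completion has drawbacks.** Participants have impaired hand function, a helping caregiver may also have assisted with GRASP, and forms sent ahead of a visit may not come back. Completing them at the visit largely deals with non-return; the other two remain as small costs.
- **That such answers lean favourable is a judgement.** The documents offer no evidence for it. This stands, and the claim here is only that they could.

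A reader might also infer something stronger from the design summary: that the questionnaires are given at the week-8 clinic visit, so that usual-care participants rate a system they have not used, or the blinded rater learns who had GRASP. The documents do not support this. The inference rests on sentence order in a short summary that leaves out the home visits altogether, and the detailed procedures place the instruments elsewhere. The two consequences also sit badly together: if both arms received the forms, receiving one would not reveal the arm. Only its content could, and only if the rater saw it before scoring was finished.

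**Conclusion.** The point holds as a minor one. Home Visit 3, as written, collects the usability and acceptance answers without provision for privacy, on tape, at a visit conducted by a non-blinded therapist who observes system use. This could bias an uncontrolled result in the hypothesised direction by an amount that cannot be estimated from the documents.

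The conclusion rests on two assumptions: that the taping sentence means what it literally says, and that at least some participants answer more kindly when not alone. It does not need the therapist to be the trainer; if so, the concern is somewhat stronger, but the documents only hint at it. The mismatch with the design summary needs a wording reconciliation. It is not evidence that the rater blind is at risk.

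**What to change.** 1. **Home Visit 3.** State that participants complete SUS, TAM and PENS themselves, in private, at the start of the visit and before the observation and the interview. Allow caregiver help where needed. The forms go into a sealed envelope for the study coordinator. Limit audiotaping to the structured interview.
2. **Statistical Considerations, question 2.** Replace the unqualified reference to subjects in the questionnaire sentence with GRASP HEP participants at Home Visit 3, so that it agrees with the procedures.

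The cost is a change of protocol wording, paper forms and envelopes, with no extra visit or staff. The downside is that some participants will need help with the forms and a few forms may be incomplete. Recording on each form whether someone helped, and who, would let the report show how often this happened.

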**3. Provide a justification for the sample size used in this protocol.**

Include sample size calculations or statistical power estimation. If not applicable, please provide explanation.

Also include the anticipated accrual rate, the accrual goal for the study, including accrual goals by strata if appropriate, adjustments for drop-outs etc. and study duration.

Answer/Response:

The first row of Table 1 provides the minimum detectable within-intervention changes in the composite Fugl-Meyer Upper Extremity (FMUE) scores that would lead 80% of the time to rejecting the null hypothesis, listed according to patient retention rate. The second row of Table 1 provides the minimum detectable between-intervention difference. Note that accounting for a 20% dropout rate, recruitment of a total of 40 subjects provides sufficient power to detect a pre- to post-intervention change of 2.4 units, a value that is consistent with previous studies of hand therapy interventions [60].

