#### **4. What is your plan for primary variable analysis?**

Include primary outcome(s)/predictor variable(s), statistical methods/models/tests to be employed, or descriptive summaries as appropriate. If not applicable, please provide explanation.

Answer/Response:

The pre- to post-intervention change in the composite FMUE score will be the primary endpoint for the Phase II efficacy study. Each of the seven tasks in the hand portion of the FMUE will be scored on a scale of 0 to 2 [53] and summed to produce a composite score. The pre-intervention scores will be subtracted from the post-intervention scores to produce a set of delta values. These delta values scores ( $\Delta$ ) will be analyzed via Analysis of Covariance (ANCOVA). One null hypothesis will test if the mean pre- to post-intervention change in the composite FMUE score is equal to zero, while the second null hypothesis will test if the mean pre- to post-intervention change in the composite FMUE score is the same for patients who undergo 8-weeks of GRASP therapy and patients who undergo 8 weeks of intensity-balanced standard care. For both null hypotheses, a  $p \leq 0.05$  decision rule will be utilized as the rejection criterion.

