#### **5. What is your plan for secondary variable analysis?**

Include the following:

--Secondary outcome(s)/predictor variables, statistical methods/models/tests to be employed, or descriptive summaries as appropriate. If not applicable, please provide explanation.  
--For phase III studies, the power/precision of the study to address the secondary objective(s).

Answer/Response:

The pre- to post intervention changes in the composite Wolf Motor Function Test (WMFT) scores will be analyzed in exactly the same way as the pre to post-intervention change in the

composite FMUE scores, and the same method of analysis will be used to analyze the pre- to post-intervention changes in Box and Blocks Test scores, and the pre- to post-intervention changes in the Motor Activity Log (MAL) scores.

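### Does the unnamed composite in the general statistical answer leave the primary endpoint open?

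*Combined protocol and SAP*

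**What the plan says.** Four answers under Statistical Considerations in the combined protocol and SAP bear on this.

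- **Question 2 (general considerations)** describes the visits, including "a battery of gold-standard UE function tests including" the FMUE, WMFT, Box and Blocks and MAL. After text on randomization, the two arms, the post-assessment and the questionnaires, it says: "The pre- to post-intervention change in the composite assessment scores will be the primary endpoint for the GRASP Phase II study".
- **Question 3 (sample size)** introduces Table 1 as giving "minimum detectable within-intervention changes in the composite Fugl-Meyer Upper Extremity (FMUE) scores", with the between-group detectable differences in the second row. It mentions no other instrument.
- **Question 4 (primary variable analysis)** says: "The pre- to post-intervention change in the composite FMUE score will be the primary endpoint for the Phase II efficacy study". It then defines the score: "Each of the seven tasks in the hand portion of the FMUE will be scored on a scale of 0 to 2", summed to one composite.
- **Question 5 (secondary variable analysis)** says: "The pre- to post intervention changes in the composite Wolf Motor Function Test (WMFT) scores will be analyzed in exactly the same way" as the FMUE, and applies the same method to Box and Blocks and the MAL.

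**The concern.** A primary endpoint should be stated once, or the same way each time. Question 2 uses a plural, names no instrument and belongs to an answer that lists four tests. The word composite does not single out FMUE, because question 5 also uses it for WMFT. Taken alone, the sentence allows three readings: FMUE only, the two scores called composite (FMUE and WMFT), or the whole battery. The plan states p ≤ 0.05 for each null hypothesis and gives no adjustment across instruments.

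The stake would be a disputed claim of success. If the FMUE hand score showed no group difference and another test did, someone might cite question 2 to say that the primary endpoint was met, while question 4 would say that it was not. Read as any one of several tests, the false-positive rate would exceed 5%.

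**Working it through.** **1. The plan's own figure.** Table 1 gives a between-group detectable difference of 2.4 units with 16 per arm (40 × 0.8 = 32, so 16 each). The documents state no SD, so the table cannot be rebuilt from stated inputs, but one can be back-solved. Assume a two-sided 0.05 level, 80% power and the normal approximation, with multiplier 1.960 + 0.842 = 2.802. The formulas are 2.802 × SD × √(2/n) between groups and 2.802 × SD / √n within a group. With SD = 2.39:

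| n per arm | 20 | 19 | 18 | 17 | 16 |
|---|---|---|---|---|---|
| within, computed | 1.50 | 1.54 | 1.58 | 1.62 | 1.67 |
| within, Table 1 | 1.5 | 1.5 | 1.6 | 1.6 | 1.7 |
| between, computed | 2.12 | 2.17 | 2.23 | 2.30 | 2.37 |
| between, Table 1 | 2.1 | 2.2 | 2.2 | 2.3 | 2.4 |

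All ten cells agree. A pooled t calculation also fits all ten, with an SD of 2.31 to 2.34. The table is therefore coherent as a calculation for one outcome with one SD. Because the SD is solved for, the fit cannot by itself establish the alpha level. That comes from the stated p ≤ 0.05 rule, and the outcome comes from question 3, which names FMUE only.

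**2. Questions 2 and 4 side by side.** Both subtract pre from post scores, analyze the differences by ANCOVA, test one null of zero mean change and one of equal change between groups, and reject at p ≤ 0.05. The differences that matter here are that question 4 names the instrument and defines its scoring. Question 2 reads as the summary and question 4 as the specification.

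**3. The plural.** Questions 3 and 5 both write of composite FMUE scores in the plural when they mean that one instrument, one score per patient. The plural in question 2 is therefore no evidence of several instruments.

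**4. The word composite.** The protocol applies it by name to FMUE and WMFT only, so Box and Blocks and the MAL do not fit it. Of those two, only the FMUE composite is given a construction (7 items × 2 points = 14 maximum), and question 5 makes WMFT secondary.

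**5. Size under the wider readings.** These figures apply only if any one significant test counted as success. At independence, four tests give 1 − 0.95⁴ = 0.185 and two give 1 − 0.95² = 0.0975. Simulation (200,000 runs, 16 per arm, two-sided t-tests at 0.05, equal correlation, no group effect) gives:

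| assumed correlation | 0 | 0.5 | 0.7 | 0.9 |
|---|---|---|---|---|
| any of four | 18.5% | 15.9% | 13.3% | 9.6% |
| any of two | 9.8% | 9.2% | 8.4% | 7.1% |

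The correlations are assumptions. Zero is implausible for arm-function measures taken on the same patients. If the battery were instead combined into one score, there would be a single test and the rate would stay at 5%. Under the FMUE-only reading there is no inflation.

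**The case for a change.** The strongest case for a change is that question 2 is current text, that its form instructions ask for the endpoints to be identified and defined, and that its own paragraph does neither. The Objectives/Hypothesis section does not help, since it speaks only of hand function and motor function. Intent gathered from neighboring answers is weaker than one consistent statement. Participants are unblinded and non-rater staff can see the randomization list, which favors wording that leaves nothing to argue about later. The edit would cost one sentence.

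Much of this stands as a drafting remark. The sentence is loose, and naming FMUE would improve it. It does not establish that the plan leaves the endpoint open. The same form has separate questions for the primary and secondary analyses, and both are answered without ambiguity. Anyone claiming success on WMFT, Box and Blocks or the MAL would have to set aside question 5. For the same reason, the sponsor would give up nothing by the edit: those tests are already secondary.

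Question 3 gives neither the scale nor the SD behind Table 1. That is a separate missing detail and does not bear on which instrument is primary.

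**Conclusion.** The concern does not call for a change. Question 2 is a less specific statement of the endpoint that question 4 defines, and questions 3 and 5 agree with question 4. An analyst working from the section as a whole would test the change in the FMUE hand score as the sole primary endpoint and report the other three tests as secondary. Rewording would leave 40 subjects, 16 per arm after 20% dropout, the 2.4-unit detectable difference and the 0.05 level as they are. The 7% to 19% error rates hold as arithmetic but describe an any-of-two or any-of-four success rule that appears nowhere in the documents. This conclusion rests on giving the dedicated answers precedence over the general one, which is how the form is organized. It does not depend on the back-solved SD or the assumed correlations.
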